8.10 Serious Adverse Events

An SAE is any adverse event that at any dose:

- results in death, or
- is life-threatening, or
- requires inpatient hospitalization or prolongs an existing hospitalization, or
- results in a persistent or significant incapacity or significant disruption of the ability to conduct normal life functions, or
- is a congenital anomaly or birth defect.

Medical and scientific judgment should be used in evaluating other AEs for seriousness, such as important medical events that may not be immediately life-threatening or result in death or hospitalization, but may jeopardize the subject or require intervention to prevent one of the outcomes defining SAEs. These events may also be considered serious. Examples of such events are intensive treatment for bronchospasm, blood dyscrasias, or convulsions that do not result in hospitalization.

All SAEs, whether judged related or not to study drug, should be reported to the Sponsor or designee by telephone, e-mail or facsimile within 24 hours of the Investigator becoming aware of such SAEs. An SAE report form will be provided for use in reporting SAEs.

The Sponsor will assess the SAE with the Investigator and determine if the SAE is reportable to relevant regulatory agencies and all other Investigators as specified in the applicable regulations, especially United States Code of Federal Regulations (CFR) Title 21 Part 312 and Guideline International Conference on Harmonization (ICH)-E2A: Clinical Safety Data Management – Definitions and Standards for Expedited Reporting. The Investigator is responsible for reporting SAEs to the IRB as per the IRB's policy.

9 DATA MANAGEMENT AND STATISTICAL CONSIDERATIONS

A separate Data Management Plan (DMP) will be generated and finalized prior to initiating data management activities. A separate Statistical Analysis Plan (SAP) will also be generated that specifies the details of all statistical analyses to be performed.

9.1 Data Management

The sponsor or their designee, will generate the CRFs. A paper or electronic CRF will be used. Velo Bio clinical study monitors will review entered data and ensure that they correspond to data kept by the site in source documents. Data management activities such as query management and coding of AE terms will be performed by the sponsor or their designee. The final quality assured data will be electronically transferred to the statistician, unless otherwise specified in the DMP.

9.2 General Considerations for Statistical Analyses

All data will be provided in listing files. Study results and information will be displayed in descriptive summary tables. All summaries, statistical analyses, and individual subject data listings will be completed using Version 9.2 or later of the SAS Statistical Analysis System (SAS Institute, Inc. Cary, NC). Unless otherwise specified all statistical analyses will be performed using $\alpha \leq 0.05$. Inference testing for treatment difference will be made specifically for the primary and key secondary outcomes. Other secondary endpoints will be assessed for treatment differences on an exploratory basis to assist with development of any future studies. No adjustments for multiplicity will be made.

All continuous data (e.g., ages, height, weight, vital signs, lab result, etc.) will be summarized by treatment group with N representing the total number of mothers (or infants) in the group, and means, standard deviations (SD), medians, minimum and maximum values.

All categorical data (e.g., race, infant gender, scores, incidences, etc.) will be summarized by treatment group with N representing the total number of mothers (or infants) in the group, and the frequency within category and the percentage within category.

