9.6 Analysis of Efficacy Outcomes

The primary outcome is the proportion of infants who have IVH grade ≥ 3 (as identified by central radiology reading) or NEC or death by 36 weeks (± 1 week) corrected gestational age. Stillbirth and fetal demise will be counted as death. An infant will achieve this composite outcome if it either is stillborn or dies or develops IVH grade ≥ 3 or develops NEC by 36 weeks (± 1 week) corrected gestational age. Because infants are likely to remain hospitalized at 36 weeks, the risk of losing an infant who would meet the outcome criteria is very small. Therefore, the reason any infant released prior to 36 weeks and subsequently lost to follow up without data at 36 weeks is likely to be due to treatment success. Such subjects will be treated as a success in the primary efficacy analysis. The composite primary outcome will be analyzed for treatment differences among the ITT analysis group, using Fisher's Exact 2-sided test for equality of proportions. To assess the sensitivity of assuming treatment success, another analysis will also be performed where all infants lost to follow-up will be assumed treatment failures.

Each of the components of the primary outcome will also be summarized and analyzed individually as secondary infant outcomes using the same statistical method as the composite.

The key secondary outcomes of this study are the change from baseline of the mother's serum creatinine levels at 24 hours post initiation of treatment and the incidence of pulmonary edema reported for the mother during the treatment period. Change from baseline serum creatinine will be assessed for treatment differences using analysis of covariance with baseline serum creatinine as covariate and treatment group as the factor.

Incidence of pulmonary edema will be analyzed for treatment differences using Fisher's Exact 2-sided test for equality of proportions.

Other secondary maternal outcomes include:

- Proportion of mothers with MEOWS ≥ 3 at 24 hours post initiation of treatment. Treatment differences will be assessed using Fisher's Exact 2-sided test for equality of proportions.
- Delivery Latency (time from initiation of treatment to delivery). This outcome will be summarized in hours and analyzed for treatment differences using a Kaplan-Meier estimation of median time to event.

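### The two key maternal secondaries get formal tests at 0.05 with no order, no dependence on the primary and no multiplicity adjustment, so one could be declared positive after the infant primary fails

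*Combined protocol and SAP*

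**What the plan says.** Section 9.2 sorts the efficacy endpoints into two classes. The first is formal: "Inference testing for treatment difference will be made specifically for the primary and key secondary outcomes". The second is not: "Other secondary endpoints will be assessed for treatment differences on an exploratory basis to assist with development of any future studies". All analyses use 0.05 unless stated otherwise, and the paragraph ends with "No adjustments for multiplicity will be made".

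Section 9.6 then gives each key secondary its own test. For the first, "Change from baseline serum creatinine will be assessed for treatment differences using analysis of covariance", with baseline creatinine as covariate and 24 hours after the start of treatment as the time point. For the second, "Incidence of pulmonary edema will be analyzed for treatment differences using" a two-sided Fisher's exact test. The primary composite is also tested with a two-sided Fisher's exact test.

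For IVH, NEC and death taken singly, Section 9.6 says: "Each of the components of the primary outcome will also be summarized and analyzed individually as secondary infant outcomes". The test is again Fisher's. The components are called secondary infant outcomes, not key secondaries.

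No section gives a hierarchy, a split of alpha, or a rule for reading the key secondaries when the primary is not significant. Section 9 announces a separate SAP for analysis detail but does not defer multiplicity to it.

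**The concern.** By separating formal from exploratory endpoints, the plan creates a family of three formal tests: one primary and two key secondaries. It then leaves that family uncontrolled. Each test stands alone at 0.05, and nothing makes the maternal results depend on the infant result.

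At stake is what may be said if the infant composite misses. On the plan's own assumptions, the primary fails with probability 1 - 0.88 = 12% to 1 - 0.76 = 24%. A creatinine or pulmonary edema result with p below 0.05 could then be reported as a formal positive finding, and the protocol would contain nothing against it. The two key secondaries together also carry more than a 5% chance of a false positive.

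**Working it through.** **Inputs.** Alpha 0.05 for every test (9.2). Three formal tests: composite by Fisher, creatinine by ANCOVA, pulmonary edema by Fisher (9.2, 9.6). 100 mothers per arm, placebo rate 20-25%, treated rate 5-10% (9.3). The pulmonary edema rate is not in the documents; 1-10% is assumed.

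**1. The plan's own figure.** Section 9.3 states 76% to 88% power at 100 per arm, and 82 to 110 per arm for 80% power. Full enumeration of the two-sided Fisher test at 0.05 gives:
- 25% vs 10%, 100 per arm: 76.2%
- 20% vs 5%, 100 per arm: 88.3%
- 20% vs 5%, 82 per arm: 80.5%
- 25% vs 10%, 110 per arm: 80.4%

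The stated figures are reproduced, and they use the full two-sided 0.05 on the primary.

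**2. Nominal family-wise error.** For k independent tests with all nulls true, it is 1 - 0.95^k.
- Two key secondaries: 1 - 0.95² = 0.0975
- Primary plus two key secondaries: 1 - 0.95³ = 0.1426

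Positive correlation lowers these. In a simulation with a common correlation of 0.3 to 0.8, two tests give 0.095 to 0.078 and three give 0.136 to 0.098.

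**3. Allowing for Fisher's actual size.** At 100 per arm and nominal 0.05, enumeration gives these sizes under the null:

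| Event rate | Actual size |
|---|---|
| 1% | 0.0004 |
| 5% | 0.021 |
| 10% | 0.029 |
| 20-25% | about 0.033 |

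With ANCOVA taken as exactly 0.05, and independence:
- Two key secondaries, edema 1%: 1 - 0.95 × 0.9996 = 0.050
- Two key secondaries, edema 10%: 1 - 0.95 × 0.971 = 0.077
- All three, edema 1%: 1 - 0.967 × 0.95 × 0.9996 = 0.082
- All three, edema 10%: 1 - 0.967 × 0.95 × 0.971 = 0.108

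**4. After the change.** If the key secondaries are tested in a fixed order only after a significant primary, each at 0.05, the family-wise error is at most 0.05. The primary is still tested at 0.05, so its power stays at 76.2-88.3%. By comparison, Bonferroni over all three (0.05/3 each) would cut primary power to 60.4-77.1%.

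**The case against.** The strongest reply is that this is a disclosed choice in a Phase 2b/3a trial with a single primary endpoint. No section calls the key secondaries confirmatory. The secondary objectives in 5.2 are maternal safety, infant safety and pharmacokinetics, so no efficacy objective rests on either endpoint. Both also recur among the outcomes of special interest in 9.7.1, under a safety section that rules out inference testing. On this view, harm arises only if the p-values are later presented as confirmatory, and because Fisher's test is conservative the excess error is small.

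Much of that stands. The excess over 5% for the two key secondaries nearly vanishes if pulmonary edema is very rare, and the primary conclusion is untouched. But 9.2 places the key secondaries beside the primary as endpoints for inference and contrasts them with exploratory ones. If nominal p-values were meant, it should say so. The announced SAP does not settle the matter: 9.2 rules adjustment out, so a SAP that added it would contradict the protocol.

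Two stronger readings are tempting, and the documents support neither:
- A reader might add the three component tests and quote 1 - 0.95⁶ = 26.5%. Under 9.2 the components fall among the exploratory secondaries. They are also nested in the composite, so independence is plainly false. They do not belong in this family.
- A reader might take the earlier antepartum trial described in Section 4 as a precedent for a positive secondary after a failed primary. That trial split two primary variables: creatinine clearance was positive and antihypertensive use was not. That is a different situation.

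**Conclusion.** The concern holds for claims on the two key secondaries. Section 9.2 states a rule that allows one of them to be declared positive at 0.05 whatever happens to the primary. A reader might infer that the primary test is compromised as well; it is not, because it is one endpoint tested once at 0.05.

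The nominal figures, 9.8% for the two key secondaries and 14.3% for all three tests, are upper values: they assume independence and exact 0.05 per test. About 5.0-7.7% and 8-11% are more realistic. These rest on independence, an exact ANCOVA level, 100 per arm and the assumed 1-10% pulmonary edema rate. The inflation is modest. The larger gap is the missing rule for reading the key secondaries after a failed primary, and closing it needs no extra subjects.

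**What to change.** Replace the no-adjustment sentence in 9.2 with a rule of this kind: the key secondaries are formally tested only if the primary composite is significant at two-sided 0.05; they are then tested in an order the sponsor fixes before unblinding (for example 24-hour creatinine, then pulmonary edema), each at two-sided 0.05, stopping at the first non-significant result. State that p-values for the components and other secondary outcomes are nominal.

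If the sponsor does not want the second key secondary to depend on the first, testing each at 0.025 after a significant primary also holds the family-wise error at or below 0.05 with no loss of primary power. If no formal key secondary claim is intended, 9.2 could instead say that those p-values are nominal.

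The cost is a text change in both protocol and SAP. Because the sentence is in the protocol, this is an amendment and goes through the IRB under 10.2. Sample size, data collection and primary power are unchanged. The real downside is that no formal key secondary claim can be made if the primary fails.

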9.2.1 Analysis Populations

The intent-to-treat (ITT) population will be comprised of all mothers and their infants who are randomized. Mothers and infants will be grouped by treatment to which they are randomized whether or not treatment was actually dispensed or whether or not it was dispensed as per the randomization assignment. All demographic baseline characteristics, and primary and secondary efficacy outcomes will be summarized and analyzed using the ITT population.

[figure not shown]
The safety population will include all ITT subjects that actually received treatment, and their treatment group will be based on drug actually received. All safety analyses will be summarized using the safety population.

The per protocol (PP) population will include all subjects in the safety population who have no major protocol violations and who have either reached an endpoint or were followed until 36 weeks (± 1 week) corrected gestational age. To assess sensitivity to protocol deviations, the primary efficacy outcome will be summarized and analyzed by the PP population.

9.3 Sample Size Considerations

The incidence of infants with either severe IVH or NEC or death within 28 days of birth in the DEEP study was 26% in the placebo group which was consistent with published incidence of 22% among a population of low birth weight infants weighing between 1250 gm and 1500 gm at birth [Horbar, et al, 2012]. A reduction in incidence of IVH/NEC/death from 25% to 10% would be considered clinically meaningful.

For purposes of sample size estimation, the expected placebo rate of IVH/NEC/death among infants is between 20-25%. The expected incidence among treated infants is assumed to be between 5-10%. A sample size between 82 and 110 mothers per treatment group would provide 80% statistical power to detect this 15-percentage point difference (see figure below).

Enrollment of 100 subjects per treatment arm is planned. The statistical power to detect a 15% treatment difference from 100 per treatment group is expected to be between 76% and 88%. The sample size and subsequent statistical power were obtained from nQuery Advisor (Statistical Solutions, LTD, V7.0) using Fishers Exact test of equal proportions.

9.4 Demographic and Baseline Characteristics

Listings and summaries of demographic and baseline characteristics will be provided for all subjects (mothers and infants).

9.5 Pharmacokinetic Analysis

The pharmacokinetics of AMAG-423 will be determined using blood samples collected at the predetermined time points. Concentration-time data for AMAG-423 will be summarized by day

with descriptive statistics at each scheduled time point. Individual and mean concentration-time profiles will be provided for each day.

Individual concentration data at actual elapsed times will be analyzed using noncompartmental methods (WinNonlin Phoenix Version 6.3 or later, Pharsight Corporation). For Dose 1 and the last administered dose, the following PK parameters will be determined (data permitting) for AMAG-423 in blood: C_{max} , time to maximum concentration (T_{max}), and area under the concentration-time curve from time zero to time of last measurable concentration (AUC_{last}). These PK parameters will be summarized using descriptive statistics for each dose.

Compartmental modeling (potentially population pharmacokinetics using NONMEM 7.3, ICON Solutions) may also be conducted if data permit such an analysis. Pharmacokinetic parameters to be estimated in such an analysis include apparent total clearance after administration (CL) and volume of distribution (V).

9.6 Analysis of Efficacy Outcomes

The primary outcome is the proportion of infants who have IVH grade ≥ 3 (as identified by central radiology reading) or NEC or death by 36 weeks (± 1 week) corrected gestational age. Stillbirth and fetal demise will be counted as death. An infant will achieve this composite outcome if it either is stillborn or dies or develops IVH grade ≥ 3 or develops NEC by 36 weeks (± 1 week) corrected gestational age. Because infants are likely to remain hospitalized at 36 weeks, the risk of losing an infant who would meet the outcome criteria is very small. Therefore, the reason any infant released prior to 36 weeks and subsequently lost to follow up without data at 36 weeks is likely to be due to treatment success. Such subjects will be treated as a success in the primary efficacy analysis. The composite primary outcome will be analyzed for treatment differences among the ITT analysis group, using Fisher's Exact 2-sided test for equality of proportions. To assess the sensitivity of assuming treatment success, another analysis will also be performed where all infants lost to follow-up will be assumed treatment failures.

Each of the components of the primary outcome will also be summarized and analyzed individually as secondary infant outcomes using the same statistical method as the composite.

The key secondary outcomes of this study are the change from baseline of the mother's serum creatinine levels at 24 hours post initiation of treatment and the incidence of pulmonary edema reported for the mother during the treatment period. Change from baseline serum creatinine will be assessed for treatment differences using analysis of covariance with baseline serum creatinine as covariate and treatment group as the factor.

Incidence of pulmonary edema will be analyzed for treatment differences using Fisher's Exact 2-sided test for equality of proportions.

Other secondary maternal outcomes include:

- Proportion of mothers with MEOWS ≥ 3 at 24 hours post initiation of treatment. Treatment differences will be assessed using Fisher's Exact 2-sided test for equality of proportions.
- Delivery Latency (time from initiation of treatment to delivery). This outcome will be summarized in hours and analyzed for treatment differences using a Kaplan-Meier estimation of median time to event.
- Antihypertensive use during treatment. This outcome will be summarized as the incidence of concomitant antihypertensive medication use once treatment has been initiated. The

incidence will be analyzed for treatment group differences using Fisher's Exact 2-sided test for equality of proportions.

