6.3.4 Randomization and Subject Identification

Randomization will occur on Day 1 after study eligibility has been confirmed. Randomization will be stratified by gestational age: ≤ 27 weeks 6/7 days and > 27 weeks 6/7 days. Study drug will be prepared and dispensed by an unblinded Pharmacist at the study site, according to the study treatment assigned by the interactive response technology (IRT) system.

A unique subject screening number, e.g. M0101, should be assigned to each subject who signs an informed consent form. In order to more easily differentiate between mother and infant, infants will be assigned the same screening number with the letter 'I' replacing the 'M', e.g. I0101. Randomization numbers will be 3 digits starting with 101. The subject screening number and randomization number should be used on all Case Report Forms (CRFs) and in all correspondence between sites, sponsor, Institutional Review Boards (IRBs), and the United States Food and Drug Administration (FDA).

Subjects will be assigned a subject randomization number just prior to dosing. This number will correspond to the blinded treatment assignment. Only qualified subjects will be assigned a subject randomization number.

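### Randomization is stratified by gestational age but the primary Fisher's exact test is not; the test is valid and its power correctly stated, yet it gives up about 4-5 points of power at the planned rates, mostly through its own conservatism

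*Combined protocol and SAP*

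**What the plan says.** Section 6.3.4: "Randomization will be stratified by gestational age: ≤ 27 weeks 6/7 days and > 27 weeks 6/7 days". Section 6.1 and the synopsis say the same and fix gestational age at consent.

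Section 9.6: "The composite primary outcome will be analyzed for treatment differences among the ITT analysis group, using Fisher's Exact 2-sided test for equality of proportions". The components use the same method, and pulmonary edema is also tested with Fisher. Change in creatinine is analyzed by "analysis of covariance with baseline serum creatinine as covariate and treatment group as the factor". None of these has a stratum term. The two sensitivity analyses of the primary endpoint (lost infants counted as failures in Section 9.6, the per-protocol population in Section 9.2.1) do not use the stratum either. In the analysis text, gestational age appears only as an optional factor for adverse-event summaries (Section 9.7). Section 9.6 names no effect estimate or confidence interval for the primary endpoint.

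Section 9.3 assumes that "the expected placebo rate of IVH/NEC/death among infants is between 20-25" percent, with 5-10% on active treatment, and states: "The statistical power to detect a 15% treatment difference from 100 per treatment group is expected to be between 76% and 88" percent. That power was calculated for Fisher's exact test.

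Section 9 defers the details of all analyses to a separate SAP, whose text is not in the supplied document.

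**The concern.** A design that balances the arms on a factor is normally analyzed with that factor. If the stratum predicts the outcome, balancing on it makes the arms more alike than the pooled 2x2 table assumes, so a pooled test becomes conservative. Fisher's exact test is conservative already, because it conditions on the total number of events and its p-values are discrete. The two effects add up.

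Power is at stake, not validity. Section 9.3 calls a fall from 25% to 10% clinically meaningful, and that is where the planned test has its lowest stated power, 76%. A SAP that follows Section 9.6 would inherit the mismatch.

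**Working it through.** **Inputs from the documents.** Two-sided alpha 0.05 (Section 9.2); 100 per arm, 1:1; event rates 20 vs 5 and 25 vs 10 percent (Section 9.3).

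**Inputs assumed.** Share of women in the early stratum 30-50%. Early-vs-late odds ratio (OR) for an event 1 to 8. Treatment odds ratio the same in both strata unless noted. Fixed 1:1 allocation within strata. Stratum rates solve s·p₁ + (1 − s)·p₂ = overall rate, with p₁/(1 − p₁) = OR·p₂/(1 − p₂).

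**Step 1. The plan's own figures.** Fisher power = Σₐ Σ_b Bin(a; 100, p_C)·Bin(b; 100, p_T)·1{Fisher p ≤ 0.05}, enumerated exactly.
- 20 vs 5: 88.3%. 25 vs 10: 76.2%. These match the stated 76-88%.
- Smallest n per arm for 80% power: 82 (80.5%) and 110 (80.4%). These match the stated 82 to 110.

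**Step 2. Fisher's conservatism alone.** The comparator is the unstratified Pearson test, X² = 200(a − b)²/[m(200 − m)] with m = a + b, also enumerated exactly.
- 20 vs 5: 92.1% against 88.3%, a loss of 3.9 points (unrounded).
- 25 vs 10: 81.6% against 76.2%, a loss of 5.4 points.

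**Step 3. Adding the stratum.** CMH without continuity correction: X² = [Σ_g(a_g − m_g/2)]² / Σ_g{n_g²·m_g(2n_g − m_g)/[(2n_g)²(2n_g − 1)]}, where n_g is the number per arm and m_g the events in stratum g. There were 200,000 simulated trials per row. Power is in percent. Differences come from unrounded values, so they may be off by 0.1.

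| Rates; early share; stratum effect | Fisher | Pearson | CMH | Pearson − Fisher | CMH − Pearson | Total |
|---|---|---|---|---|---|---|
| 20 vs 5; 40%; none | 88.3 | 92.1 | 92.2 | 3.9 | about 0 | 3.9 |
| 20 vs 5; 40%; placebo 35/10, active 8.75/2.5 | 89.0 | 92.8 | 93.2 | 3.8 | 0.4 | 4.2 |
| 20 vs 5; 30%; OR 8 | 89.7 | 93.3 | 94.5 | 3.6 | 1.1 | 4.8 |
| 25 vs 10; 40%; none | 76.1 | 81.6 | 81.1 | 5.4 | −0.4 | 5.0 |
| 25 vs 10; 40%; placebo 40/15, active 16/6 | 76.8 | 82.2 | 83.2 | 5.4 | 0.9 | 6.3 |
| 25 vs 10; 50%; OR 8 | 77.4 | 83.0 | 85.3 | 5.5 | 2.3 | 7.8 |
| 25 vs 10; 30%; OR 8 | 77.8 | 83.4 | 86.7 | 5.6 | 3.3 | 8.9 |

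The second and fifth rows hold the risk ratio constant (0.25 and 0.4). Their placebo stratum ORs are (0.35/0.65)/(0.10/0.90) = 4.8 and (0.40/0.60)/(0.15/0.85) = 3.8. Over the whole grid, stratifying adds about 0 to 1.3 points for OR up to 4 and at most 3.3 at OR 8. The split depends on the form of the effect. With placebo 40/15 and a constant 15-point difference (active 25/0), CMH adds 2.8 points over Pearson and the total is 8.3.

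**Step 4. Two-sided size under the null, common rate 20-25%.**

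| Stratum effect | Fisher | CMH |
|---|---|---|
| None | 3.3-3.4% | 4.9-5.1% |
| OR 4 | 2.6-2.7% | 4.9-5.1% |
| OR 8 | 1.8-2.3% | 4.9-5.1% |

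Over all null scenarios run, CMH size was about 4.9-5.3%.

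**Step 5. Dependence on the version of the stratified test.** An exact conditional stratified test (20,000 trials per scenario) gains only about 0 to 4 points over Fisher. A continuity correction removes most of the CMH gain: in the fifth row of Step 3, CMH falls from 83.2% to 77.8%, against 76.8% for Fisher.

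**The case against.** The planned test is a defensible choice. Its size is guaranteed not to exceed 5%, power was calculated for the same test, and Section 9.3 openly gives both the 76% figure and the 110 per arm needed for 80%. All of this stands.

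Four stronger readings are tempting, and the documents do not support them.
- That 4-9 points are lost because the strata are ignored. Steps 2 and 3 show that most of the loss would remain if there were no strata at all. The upper end needs 25 vs 10 together with a stratum odds ratio near 8 or an equally strong assumption about the effect. At 20 vs 5 the total stays below 5 points.
- That only a stratified test exceeds 80% power at 25 vs 10. The unstratified Pearson test already reaches 81.6%.
- That false positives are inflated or the power overstated. The size lies below 5%, and the stated power already includes the conservatism.
- That gestational age was chosen as stratum because it drives the composite. No reason for the stratification is given; Section 4 links death, IVH and NEC to very low birth weight. A strong stratum effect is plausible but remains an assumption.

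The deferral to a separate SAP also limits what can be called absent. A stratified sensitivity analysis or a confidence interval may be intended there. It does not remove the core point, because Section 9.6 already fixes the primary test and the ANCOVA terms.

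**Conclusion.** The mismatch between stratified randomization and unstratified efficacy analyses is real in the protocol text. On the documents' own rates, the planned test gives up about 4 points (20 vs 5) to 5 points (25 vs 10) against uncorrected CMH. For scale, the 25 vs 10 gain is about what ten more women per arm would bring: Fisher needs 110 per arm for 80.4%, while CMH has 81.1% at 100. A prognostic stratum can raise the loss at 25 vs 10 to about 9 points, under assumed shares and odds ratios.

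No loss was calculated for the creatinine ANCOVA, pulmonary edema or the individual components, and the documents do not show that gestational age predicts the maternal outcomes. For these the point is consistency with the design. Overall this is a recommended improvement, not a must-fix.

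**What to change.** Before unblinding, amend Section 9.6 and write the SAP to match:
- Primary analysis: CMH test in the ITT population, stratified by the gestational-age stratum used at randomization, stated explicitly as without continuity correction.
- Estimate: Mantel-Haenszel common risk difference with 95% CI.
- Sensitivity analysis: the present Fisher's exact test.
- Creatinine: add the stratum as a factor in the ANCOVA.
- Components and pulmonary edema: a stratified test, in its exact version where events are sparse. Little power gain should be claimed for these.
- Section 9.3: say that the 76-88% refers to Fisher's test, or restate power for the new primary test with its stratum assumptions.

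The cost is wording only, with no extra women or data. The small downside is that CMH is asymptotic: with 20 + 5 = 25 to 25 + 10 = 35 expected events its simulated size is about 5%, but it lacks Fisher's guarantee. If the sponsor prefers that guarantee, a prespecified stratified sensitivity analysis is the minimum.
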